serological criteria, will be recruited for this study. 42 will undergo oral immunotherapy, while 42 will be followed as natural history controls but will be offered similar therapy, should it be successful, at the completion of one year. OIT subjects will initiate therapy with a 2-day rush desensitization treatment using oral doses of milk, in our Clinical Investigation Unit. They will then continue the highest tolerated dose of milk at home for two weeks. Subsequently, they will return for weekly increases in doses until a maximum of 200 ml of milk is ingested daily. The primary clinical outcome will be a comparison of the amount of milk consumed safely on oral challenge performed prior to OIT, when the OIT dose has reached its maximum (200 ml or highest tolerated dose) and after one year of therapy. Patients will also be followed with clinical symptom scores and adverse event diaries and we will monitor immunological parameters such as changes in milk-specific IgE, blocking antibodies (IgG4 and IgA) and regulatory T and B cells. We expect that we will be able to see important improvement in the ability to safely ingest milk and other dairy products, and this will be accompanied by significant decreases in IgE and increases in Regulatory T and B cells.

BACKGROUND INFORMATION:

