1.0 Food allergy, a common, significant problem: Foods are reported to be extremely common triggers of anaphylaxis, accounting for 33.2% to 56% of all anaphylaxis cases (1, 2). Food-induced anaphylaxis is an increasing reason for hospital admission, primarily in the first 2 decades of life. At present, the only treatment for food allergy is to avoid the causative food, while the principle treatment for an allergic reaction is prompt administration of intramuscular epinephrine (3, 4). Cow milk allergy (CMA) is the most common food allergy in children. CMA is associated with severe and frequent allergic reactions, life-threatening anaphylaxis, and multiple nutritional deficiencies. Due to the ubiquitous use of cows' milk in Western diets, it is almost impossible to avoid (5). Studies suggest that quality-of-life of patients and families with milk allergy is highly impaired (6). The large burden of this disease requires development of new treatment strategies apart from avoidance to alleviate this problem. This proposal will examine oral immunotherapy to cow's milk as a treatment for CMA. We will perform the first Canadian placebo-controlled trial of milk oral immunotherapy (OIT), and evaluate the clinical and immunological parameters that will help determine the ideal protocols, and predict ideal candidates to have maximal impact of this treatment strategy on the large population of children and adolescents with CMA in Canada.

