4.0. Statistical Considerations

A: Sample Size calculation: Given that previous studies have attributed at least 50% improvement in the ability to tolerate milk(24) with an α of 0.05 and a power (1- β) of 0.80, a sample of 42 cases and 42 controls will be recruited.

B: Statistical Analysis: Statistical analyses will be performed using paired t-tests. A p value of <0.05 will be considered significant. Descriptive statistics of the variables including means, standard deviations and frequencies were computed for all study variables. The concentrations of milk –specific IgE, IgG and IgA, the size of the skin tests , T reg and Breg expression at the different study time-points will be compared with their baseline values using the one-sample paired t-test and to the control using a 2 sample t-test .

Multiple regression models will be used to assess factors associated with response to desensitization, including baseline demographic characteristics; gender; age; baseline SPT and specific IgE, Treg and Breg numbers, and vitamin D level.

5. Ethical Considerations

In the consent form given at study enrolment, participants will be advised that they will be randomly assigned to either oral immunotherapy or observation for a one year period. Participants will also be advised that their data will be shared only among the OIT study team. Participants in the observation control group who will not receive OIT treatment, will be told that they may to undergo such therapy after a year of observation and a positive oral food challenge.

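### An unspecified regression on at least seven baseline factors in about 42 treated children is at high risk of over-optimistic prediction and false predictors

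*Combined protocol and SAP*

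**What the plan says.** Section 4.0 B states that "Multiple regression models will be used to assess factors associated with response to desensitization", the factors "including baseline demographic characteristics; gender; age; baseline SPT and specific IgE, Treg and Breg numbers, and vitamin D level". Seven are named: gender, age, skin prick test, milk-specific IgE, Treg, Breg and vitamin D. The demographic characteristics are left open, so seven is a minimum.

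The only significance rule in the section is p<0.05. For the regression, the section gives no outcome, model type, analysis set, limit on terms, selection rule, shrinkage, internal validation or multiplicity rule. It does not label the results exploratory.

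On numbers, section 4.0 A says "a sample of 42 cases and 42 controls will be recruited", and the Experimental Approach says "42 will undergo oral immunotherapy, while 42 will be followed as natural history controls". Section 3.3.6 defines the response in three categories and counts only total desensitization as success. The paragraph on withdrawal from therapy foresees losses from treatment, but no dropout rate is given.

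On purpose, section 1.0 of the background says that the trial will help to "predict ideal candidates to have maximal impact of this treatment strategy". The project summary and the rationale in section 2.2 also speak of understanding which patients are ideal and of passing protocols on to practitioners.

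**The concern.** Response to immunotherapy can be observed only in children who receive it, so this analysis rests on about half of the 84 recruited. An unpenalised regression with many terms and few outcomes fits the chance features of its own sample. Its apparent discrimination is then too high, and its predicted probabilities are too extreme for new patients.

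A second, separate problem is that each factor can be called significant at p<0.05 with no allowance for the number of factors tested.

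The stake is the trial's message about whom to treat. A model that looks predictive without being validated, or a single factor that crosses p<0.05 by chance, could be passed on to practitioners as a criterion for choosing candidates. The plan contains nothing that would warn the reader of either.

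**Working it through.** **Inputs from the documents.** 42 treated and 42 controls; at least 7 predictors; p<0.05; success is binary (total desensitization or not).

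**Assumptions, because the documents give no figures.** Success rate 30% to 80%. Loss of treated subjects 0% to 20%, so 42 × 0.8 = 33.6, about 34, to 42 analysable. For the case with real signal, three true predictors with log-odds of 1.0, 0.7 and 0.5 per SD and four null ones.

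**The plan's own figure.** Section 4.0 A derives 42 per arm "with an α of 0.05 and a power (1- β) of 0.80" from "at least 50% improvement in the ability to tolerate milk". This cannot be reproduced, because the scale and the control rate or SD are not stated. A 42 does arise from unstated inputs such as 30% against 60%. The figure was not set for the regression, and the point here does not depend on how it was derived.

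**Step 1: events per predictor.** This is n × min(success rate, 1 − success rate) ÷ 7.

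| n analysed | 50% success | 30% or 70% | 80% |
|---|---|---|---|
| 42 | 21/7 = 3.0 | 12.6/7 = 1.8 | 8.4/7 = 1.2 |
| 34 (20% loss) | 17/7 = 2.4 | 10.2/7 = 1.5 | 6.8/7 = 1.0 |
| 84 (all controls treated later and pooled) | 42/7 = 6.0 | 25.2/7 = 3.6 | 16.8/7 = 2.4 |

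**Step 2: optimism of a joint logistic model.** All seven terms were entered, with 800 simulated datasets per setting and predictor correlation 0.2.

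- n = 42, no true predictor: fitted AUC 0.74 at 50% success, 0.75 at 30% or 70%, and 0.79 at 80%. AUC in new data is 0.50 throughout.
- n = 42, three true predictors: fitted AUC about 0.88, new-data AUC 0.73 to 0.76, calibration slope 0.33 to 0.45. A second simulation of the same kind gave 0.86 against 0.73, with slope 0.41 to 0.44.
- n = 34, three true predictors: new-data AUC 0.69 to 0.73, slope 0.21 to 0.34, and complete separation in 2% to 15% of datasets.
- n = 84, three true predictors: new-data AUC 0.78 to 0.80, slope 0.65 to 0.72.

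A slope of 1 means that predictions are correctly scaled. A slope below 0.5 means that differences between patients on the log-odds scale are overstated more than twofold.

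**Step 3: the same question with a continuous response.** With no true predictor, expected R² = 7/(42 − 1) = 0.17. With a true R² of 0.2, 0.3 and 0.5, the fitted R² is 0.33, 0.41 and 0.58, and the new-data R² is 0.01, 0.13 and 0.38. Power to detect the strongest factor is 60%, 80% and 99%.

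**Step 4: multiplicity.** For seven independent tests, the chance of at least one p<0.05 with no true predictor is 1 − 0.95^7 = 1 − 0.698 = 0.302. The logistic simulations at n = 42 gave 25% to 32%. A simulation with independent predictors gave 29% to 30% at both n = 42 and n = 4200, so this risk does not come from the small sample.

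**The case against.** A reader might infer that the regression is certain to overfit, that its findings would be mostly noise, and that no more than 42 children can contribute. The documents do not support any of these as stated.

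- **Certain overfitting.** Section 4.0 B speaks of models in the plural and does not say that all factors enter one of them. It does not name logistic regression either. The Experimental Approach describes the primary outcome as the amount of milk safely consumed. With that as a continuous response, each coefficient test in a linear model keeps its nominal 5% level, and a strong factor can be found (step 3).
- **Mostly noise.** This follows only if little truly predicts response. With the assumed moderate predictors, the model still discriminates in new data. It is over-optimistic and badly calibrated, but it is not empty.
- **No more than 42.** The design is called cross-over, and controls may be offered treatment later (section 3.3.4, Control Subjects, and section 5). The plan does not say that they would be pooled. Even 84 leaves only 2.4 to 6.0 events per predictor, so this changes the wording and not the substance.
- **False predictors as a small-sample effect.** The 30% figure is multiplicity and would be the same in a large trial. It should not be cited as evidence of overfitting.

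It is also fair to say that prediction is not among the four specific objectives in section 2.1, and that section 4.0 B promises only to assess association. That limits the weight of the point. It does not remove it, because the stated purpose of finding ideal candidates has no other analysis behind it.

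**Conclusion.** The concern holds as a conditional one. The regression is not specified, and its most direct reading is a joint model of "baseline SPT and specific IgE, Treg and Breg numbers, and vitamin D level" with age, gender and other demographics on the success outcome of section 3.3.6. With about 42 treated children, that model would have 1.2 to 3.0 events per predictor over assumed success rates of 30% to 80%.

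Its apparent AUC would exceed the new-data AUC by about 0.24 if nothing predicts response (0.74 − 0.50 at 50% success). Under the assumed moderate signal the excess is about 0.12 to 0.15 (0.88 − 0.76 to 0.88 − 0.73). Independently of this, there is about a 30% chance of naming at least one false predictor if none is real.

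The success rates, losses and effect sizes are assumptions, and the direction of the result is the same across all of them. This is a worthwhile and inexpensive improvement to a secondary analysis. It does not touch the randomised comparison.

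**What to change.** In section 4.0 B:

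1. State the outcome (total desensitization as defined in section 3.3.6) and the analysis set (the treated arm of the randomised comparison). Say how withdrawals are handled, and that controls treated later are not pooled unless this is specified in advance.
2. Fit the listed baseline factors in one ridge-penalised model, with the demographic terms listed in full. Alternatively, limit the model to two or three predictors named in advance. Which ones is the investigators' choice. With three predictors at n = 42 there would be 21/3 = 7.0 events per predictor at 50% success and 12.6/3 = 4.2 at 30% or 70%, so validation is still needed.
3. Report bootstrap optimism-corrected discrimination and calibration with confidence intervals.
4. Label the predictor findings exploratory, and state that no single p<0.05 will be taken as identifying ideal candidates.

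Firth correction should not be offered as equivalent to ridge. In simulation at n = 42 with no true predictor, it left the apparent AUC almost unchanged (0.73 with and without it at 50% success; 0.75 against 0.76 at 70%), although Wald false positives fell.

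The cost is a few sentences in the plan, a little more analysis work, and less favourable apparent model performance. No further subjects, visits or assays are needed.

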Through a process of stratified randomization (according to sex), participants will be randomly assigned to one of 2 study groups. The first group will receive active desensitization, and the second group will not receive any treatment but will be followed up regularly (Appendix A Table 2). Desensitization will be offered to the observation groups following the trial, should the outcome be successful in the treatment group.

3.2 Oral challenge test to milk. Prior to initiating desensitization and following treatment, the subjects will undergo a placebo controlled oral challenge to milk. These challenges will determine the level at which the children react and will be the baseline to follow their improvement in oral tolerance following therapy.

Oral challenges will be single blinded and will be performed with fresh cow's milk, with increasing doses taken orally every 10 to 15 minutes up to a total of 150ml of milk (doses of 0.1, 0.3, 1.0, 3.0, 10.0, 30.0, 45ml, 60 mL) ^{(49,82) (83)}. Patients will receive 2 challenges per day, 1 placebo and 1 with the active substance (milk). Nurses in the Medical Day Unit/Center for Investigative Medicine will prepare the food and randomize the placebo challenges. Unless contraindicated, the placebo will be soy or rice-based milk. If the challenge is negative after 150 ml of milk, results will be confirmed by means of open challenge, using 250ml of yogurt or ice cream 1 hour after completion of the blinded portion(29) according to the recommendations of the European Academy of Allergology and Clinical Immunology (5). After completing the challenge, patients will be kept under observation for at least 2 hours. Only objective symptoms will be considered to be indicative of a positive allergic reaction (29). Food challenges will be scored as positive if a single symptom or any of the following objective clinical reactions will be observed: urticaria, angioedema, wheezing, rhinitis, vomiting, diarrhea, protracted abdominal pain, exacerbation of atopic dermatitis, or shock. A single episode of vomiting will not be considered as a positive reaction, while severe and repetitive vomiting will. If the challenge is **negative**, ie, the subject is asymptomatic, he/she will be excluded from the study. Based on our experience, approximately 80% of those subjects ages 6 or greater, with positive history and positive skin tests, approached will fail the oral challenge and thus be eligible.

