Withdrawal from therapy: Subjects will be carefully monitored during the in hospital rush therapy phase, as well as during the home OIT phase. Instructions for treatment of reactions will be provided as above. Patients who are enrolled will be informed that in previously published studies, minor allergic reactions are common in these protocols (mild itching, abdominal discomfort) but resolve with increased time on therapy. Subjects will be withdrawn if they cannot tolerate the low dose, rush desensitization phase, if they have more than 2 or more moderate or severe reactions during the home (maintenance) OIT phase, if they experience a rare or unforeseen complication such as severe flares of eczema or chronic gastrointestinal symptoms (e.g. development of eosinophilic esophagitis) and if the parents or subjects wish to voluntarily terminate therapy.

3.3.6 : Variables measured. The following variables will be measured in each patient:

A. The primary outcome measure will be the presence of desensitization defined by the ability to tolerate 200 ml of milk 1 year after the start of the trial. This is a qualitative variable with three categories: total desensitization (200 mL of cow's milk); partial desensitization (20–200 mL); and failed desensitization (<20 mL milk). Only patients presenting total desensitization were regarded as being successfully desensitized.

B. Secondary outcome measures will be:

1. Number and severity of adverse reactions occurring after oral exposure to milk during the desensitization and follow-up phases.
2. Minimum dose of milk that triggered symptoms during the desensitization protocols or challenge tests.
3. Days until desensitization was achieved.
4. Indices of desensitization :
 - a. Change in skin prick test weal size, comparing tape transferred, cpoputor measured diameters and areas of the skin tests to milk extract.
 - b. Levels of sIgE, sIgA and sIgG4 before desensitization, during follow-up and at the end of the study.
 - c. T and B reg before desensitization, during follow-up and at the end of the study.

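### Section 4.0 B names no between-arm analysis of the milk-challenge outcome and does not list the baseline eliciting dose as a covariate

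*Combined protocol and SAP*

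**What the plan says.** Section 3.2 on the pre-treatment challenge: "These challenges will determine the level at which the children react", and the result "will be the baseline to follow their improvement in oral tolerance following therapy". A child with a negative challenge is excluded, so every child who stays in the study has a reaction level on record.

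The primary outcome is stated in two ways. The Experimental Approach paragraph says: "The primary clinical outcome will be a comparison of the amount of milk consumed safely on oral challenge performed prior to OIT", set against the amounts at maximum dose and after one year. Section 3.3.6 A instead takes desensitization, "defined by the ability to tolerate 200 ml of milk 1 year after the start of the trial", in three categories cut at 20 and 200 mL. The second definition makes no use of the starting dose.

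Section 4.0 B has three relevant parts:

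- A general sentence assigns paired t-tests, without naming an outcome.
- A comparison with baseline (paired) and with control (two-sample t-test) is named for milk-specific IgE, IgG and IgA, skin-test size, Treg and Breg.
- A multiple regression for response to desensitization has an open-ended predictor list of demographics, sex, age, "baseline SPT and specific IgE, Treg and Breg numbers, and vitamin D level".

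The challenge dose is named in none of the three. Randomisation (end of section 3.1) is stratified by sex only.

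**The concern.** The reaction level at entry is the plan's own direct measure of how allergic a child is, and the outcome is the same kind of measurement a year later. The entry level can vary widely, while the outcome is judged against fixed cut-offs of 20 and 200 mL. An analysis that ignores the entry level mixes where a child started with how the child responded.

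Three things are at stake:

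- **Missing analysis.** The plan does not say how the arms will be compared on the outcome that carries the efficacy objective. The analyst would have to choose after the data are in.
- **Precision.** With 42 per arm and stratification by sex alone, some chance imbalance in entry dose is likely, and without adjustment its share of the outcome variance stays in the error term.
- **Interpretation of predictors.** Finding the ideal patients is a stated aim. If entry dose is not in the response model, an apparent effect of IgE or skin-test size may partly reflect the starting threshold.

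**Working it through.** **1. The plan's own figure.** Section 4.0 A states "a sample of 42 cases and 42 controls will be recruited", "with an α of 0.05 and a power (1- β) of 0.80", for an improvement of at least 50%. It gives no control rate, SD, scale for the 50% or sidedness, so 42 cannot be derived from the stated inputs. Two-sided results per arm under different readings are: 0.5 SD difference, 63; absolute 50-point difference, 11 to 15; 50% to 75%, 58; 20% to 50%, 39 (39/0.95 gives 42 if 5% dropout is added, but the plan states no dropout). Nothing below depends on how 42 was reached. It is taken as given.

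**2. Spread of the baseline.** The challenge steps in section 3.2 run from 0.1 to 60 mL. The ratio is 60/0.1 = 600, or log10(600) = 2.78, nearly three orders of magnitude. A child who tolerates the 30 mL step and reacts at 45 mL has already taken 0.1 + 0.3 + 1 + 3 + 10 + 30 = 44.4 mL without reaction. On cumulative amount, that child is in the 20–200 mL partial band of section 3.3.6 before any treatment.

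**3. Chance imbalance.** The standard error of the between-arm difference in mean baseline (log scale, SD units) is √(2/42) = 0.218. About one trial in twenty would show a gap above 1.96 × 0.218 = 0.43 SD.

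**4. Gain from adjustment.** The correlation r between log baseline dose and the one-year outcome is an assumption, shown over 0.3 to 0.7. The outcome is treated as continuous and compared on follow-up values, two-sided α = 0.05.

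- Residual variance factor: 1 − r².
- Difference detectable with 80% power unadjusted at 42 per arm: (1.96 + 0.84) × √(2/42) = 0.61 SD.
- Power for that difference after adjustment: Φ(2.80/√(1 − r²) − 1.96). At r = 0.5: 2.80/0.866 = 3.235, less 1.96 is 1.275, and Φ = 0.90.
- Number per arm that would keep 80% power: 42 × (1 − r²), rounded up.

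| Assumed r | 1 − r² | Variance removed | Power, 0.61 SD | Per arm for 80% | Power, 0.5 SD (63% unadjusted) |
|---|---|---|---|---|---|
| 0.3 | 0.91 | 9% | 84% | 39 | 67% |
| 0.5 | 0.75 | 25% | 90% | 32 | 75% |
| 0.7 | 0.51 | 49% | 97.5% | 22 | 89% |

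**5. If the comparison were on change from baseline.** With equal variances at both times, a change score has variance factor 2(1 − r): 1.4, 1.0 and 0.6. The ratio of adjusted to change-score variance is (1 − r²)/(2(1 − r)) = (1 + r)/2: 0.65, 0.75 and 0.85. Adjustment still helps, but the pattern reverses: the reduction is 35%, 25% and 15%, largest at low r. The table in step 4 therefore does not apply to change scores.

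**The case against.** **The baseline amount is used.** A reader might infer that the challenge dose enters no comparison at all. The documents do not support that. The Experimental Approach paragraph makes the pre-treatment amount one side of the primary comparison, and the general paired t-test sentence could cover it. This stands. But a paired test within the treated arm is not a comparison with control.

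**The two-sample t-test belongs to other variables.** It is also tempting to read section 4.0 B as prescribing an unadjusted t-test between arms for tolerated amount. It does not; that test is named for antibodies, skin tests and regulatory cells. For the challenge outcome, no between-arm test is named at all.

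**The predictor list is open.** The baseline dose is unlisted, not excluded. That is right, but an open list does not prespecify it.

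**Randomisation protects the comparison.** An unadjusted analysis would be unbiased, so adjustment is a matter of efficiency. This stands and limits the severity.

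**The importance of the covariate is a judgement.** No correlation is given, and clustering of treated children at the 200 mL target could weaken it. Whether entry dose confounds the IgE effect or lies on its path to response is a modelling question. Both stand, so the interpretive concern is a possibility and not a demonstrated bias.

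**Cost in the response model.** Seven predictors are named besides general demographics. For about 42 treated children that is 42/7 = 6 per predictor; an eighth makes it 42/8 = 5.25. This is a real but small cost.

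**Control-arm follow-up.** The control-subject paragraph lists skin tests, blood tests and diaries but no challenge. Section 5 does refer to a positive challenge after the year of observation, so the data seem intended, though the scheduling is not spelled out.

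**Conclusion.** The point holds as a gap in prespecification with a likely loss of precision. It does not show a biased analysis. The plan collects the baseline eliciting dose and relies on it descriptively, but specifies neither a between-arm analysis of the challenge outcome nor a place for that dose as a covariate. The missing analysis is the larger part; the covariate is a nearly free improvement to it.

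The gain ranges from modest at r = 0.3 to large at r = 0.7. These figures rest on an assumed r, a continuous outcome, a linear relation on the log scale and comparison of follow-up values. A reader might take the same gains to apply to the three-category primary outcome of section 3.3.6. They do not transfer directly, because variance reduction by r² is a property of the linear model.

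**What to change.** 1. Reconcile the Experimental Approach paragraph with section 3.3.6 A, so that one primary outcome stands.
2. In section 4.0 B, name the between-arm analysis of the one-year challenge outcome: a linear model for log tolerated amount, or a logistic or ordinal model for the section 3.3.6 categories. If the model is logistic or ordinal, state the effect measure to be reported, since a covariate-adjusted odds ratio differs in meaning from an unadjusted one.
3. Prespecify log baseline eliciting dose as a covariate in that model. Define it as the challenge step at which the child reacted. The smallest step is 0.1 mL, so the log always exists. Cumulative mL tolerated is a different quantity and is zero for a child who reacts at the first step, so its log is undefined. The same problem arises if log tolerated amount is the outcome, and a convention for zero is needed there. State also the value for a child who reacts only at the open challenge.
4. Name the baseline eliciting dose among the predictors in the response-to-desensitization regression. This does not replace item 3, because that regression is not the comparison of arms.
5. Confirm in the control-subject paragraph that the one-year challenge mentioned in section 5 is done for all controls.

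The baseline value is already collected, so items 1 to 4 cost only wording, plus one more term in a response model that is already full for about 42 treated children. Item 5 costs nothing if the control challenge is already planned, as section 5 suggests.
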